2 INTRODUCTION

This statistical plan addresses the planned analyses for the study on the MANTIS Clip Study based on the protocol dated February 17, 2023 Version C. Specified analyses may be used for scientific presentation and/or manuscripts and may not all be provided to Competent Authorities.

ENDPOINT ANALYSIS

3.1 **Primary Endpoints**

3.1.1 Primary Effectiveness Endpoint

Clinical Initial Cohort

Ability to complete the indication for the use of endoscopic clipping

Continued Enrollment Cohort

Clinical success defined as, where applicable,

- Absence of delayed bleeding
- Sustained closure of the targeted lesion (up to 30 days after the endoscopic clipping procedure)

3.1.2 Primary Safety Endpoint

Rate of serious adverse events (SAEs) related to the MANTISTM clip or the endoscopic study portion of the procedure.

NOTE: If providing hemostasis to an active bleeding in Group A requires possible additional hemostasis after the index study procedure for management of bleeding SAEs within 7 days of the index study procedure, then such bleeding SAEs are not counted for the Primary Safety Endpoint.

3.1.3 Hypotheses and Sample Size

Initial cohort:

No hypotheses will be tested, only observational, summary statistics will be performed.

Continued enrollment cohort:

A systematic literature search was conducted on PubMed and Embase from January 1, 2016 to September 2022 to identify studies that evaluated the safety and effectiveness of an endoscopic clip device for closing various types of incisions, lesions, or defects in the gastrointestinal tract resulting from endoscopic mucosal resection (EMR), endoscopic submucosal dissection (ESD), polypectomy of polyps or adenomas, perforations, and fistulas. The primary objective of the search strategy was to identify studies that examined the closure of large mucosal defects by endoscopic clipping. Twenty studies

were identified through a post-market literature review activity were included to the analysis with a total of 2257 patients.

We hypothesize that the **clinical success rate** of MANTISTM clip will be greater than the performance goal of **89%** with expected clinical success rate of **94%**. These assumptions are based in the following meta-analyses of clinical success for closure of a defect:

• 20 publications representing 2257 patients: 93.9% (95% CI 88.6%-97.6%)

The null and alternative hypotheses for the primary effectiveness endpoint are as follows:

Ho: $\pi_1 \le 89\%$ *Ha*: $\pi_1 > 89\%$

where π_1 is the probability of clinical success.

We hypothesize that the **serious adverse event (SAE) rate** related to MANTISTM clip or the endoscopic clipping portion of the procedure will be lower than the performance goal of **19%** with expected related SAE rate of **10%**. These assumptions are based in the following meta-analyses of clinical success for closure of a defect:

• 9 publications representing 1019 patients: 9.8% (95% CI 3.7%-18.5%)

The null and alternative hypotheses for the primary endpoint are as follows:

Ho: $\pi_1 \ge 19\%$ *Ha*: $\pi_1 < 19\%$

where π_1 is the probability of an related SAE.

Using an exact test with an alpha level of 0.05, 217 subjects enrolled will provide at least 80% power for the performance and safety metrics. An additional 10% will be added for attrition, so total enrollment will be 240 subjects. These tests will only be performed for cases in the continued enrollment cohort

4 GENERAL STATISTICAL METHODS

4.1 Analysis Sets

Enrolled Cohort

A subject is considered enrolled after signing the study-specific ICF. Subjects who sign the ICF, but subsequently do not meet one or more of the eligibility criteria provided in Section 8.1 and Section 8.2 will be considered screen failures and excluded from the study.

Intent-to-Treat Cohort (ITT)

This cohort consists of enrolled subjects who are planned to have a MANTISTM clip placed regardless if they met I/E criteria.

Treated Cohort

The treated cohort is a subset of the ITT subjects who have a MANTISTM clip placed.

ADDITIONAL DATA ANALYSES

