9.1 Inclusion Criteria

Subjects who meet all of the following criteria (see Table 9.1-1) may be given consideration for inclusion in this clinical investigation, provided no exclusion criterion (see Section 9.2) is met.

Table 9.1-1: Inclusion Criteria

Inclusion Criteria

- 1. Subject indicated for endoscopic clipping per local standard of practice.
- 2. Willing and able to comply with the study procedures and provide written informed consent to participate in the study

NOTE: Hemostasis and closure can be needed in the setting of complications such as perforations or acute bleeding that are typically rare and sometimes emergent. In such circumstances consenting the patient before the procedure is not feasible and consent shall be obtained from the patient after the procedure but before any study data is collected.

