9.2 Exclusion Criteria

Subjects who meet any one of the following criteria (Table 9.2-1) cannot be included in this study or will be excluded from this clinical study. No vulnerable populations will be enrolled in this study per the local standard of care at the institution/IRB.

Table 9.2-1: Exclusion Criteria

Exclusion Criteria

- 1. Subjects who are currently enrolled in another investigational study that would directly interfere with the current study, without prior written approval from the sponsor
- 2. Subjects who the investigator deems at risk for study device or procedure related complications per the Instructions for Use (IFU) where commercially available or the Investigator Brochure (IB) for countries where the study device is not approved.

10 Subject Accountability

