10.1 Point of Enrollment

Subjects will be considered enrolled into the study at the time of the study-specific Informed Consent Form (ICF) execution. Subjects who have signed informed consent but do not undergo the study procedure are considered screen failures. Screen failures will be recorded

in the Electronic Data Capture (EDC) system by each study site and will not count toward total study enrollment.

In the case it is determined that the subject failed to meet the inclusion/exclusion criteria after the subject has agreed to participate in the study and has signed the informed consent, the study personnel will complete the Screening form and the End of Study form.

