12.2.1 Analysis Sets

Enrolled Cohort

A subject is considered enrolled after signing the study-specific ICF. Subjects who sign the ICF, but subsequently do not meet one or more of the eligibility criteria provided in Section 8.1 and Section 8.2 will be considered screen failures and excluded from the study.

Intent-to-Treat Cohort (ITT)

This cohort consists of enrolled subjects who are planned to have a MANTISTM clip placed regardless if they met I/E criteria.

Treated Cohort

The treated cohort is a subset of the ITT subjects who have a MANTISTM clip placed.

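### Screen-failure rule and ITT definition conflict for treated subjects later found ineligible, and no analysis set is named for the two primary tests

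*SAP*

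**What the plan says.** - **Screen failure, analysis-set sections.** SAP 4.1 and protocol 12.2.1 carry the same text. It covers people who have given consent and then "subsequently do not meet one or more of the eligibility criteria provided in Section 8.1 and Section 8.2". The stated consequence is that they "will be considered screen failures and excluded from the study". No cut-off is given. The criteria are actually in protocol 9.1 and 9.2; 8.1 and 8.2 cover scale, duration and design justification.
- **ITT, next paragraph.** "This cohort consists of enrolled subjects who are planned to have a MANTISTM clip placed regardless if they met I/E criteria". The Treated cohort is the part of ITT in whom a clip was placed.
- **Screen failure, protocol 10.1.** "Subjects who have signed informed consent but do not undergo the study procedure are considered screen failures". For ineligibility found after consent, "the study personnel will complete the Screening form and the End of Study form", again without a time limit.
- **Emergent cases, protocol 9.1.** "consent shall be obtained from the patient after the procedure but before any study data is collected".
- **Population for the tests, SAP 3.1.3.** "These tests will only be performed for cases in the continued enrollment cohort". That names a recruitment phase. No passage assigns the Enrolled, ITT or Treated set to either test.

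**The concern.** A subject who consents, receives a clip and is later found ineligible is out of the study under one paragraph of SAP 4.1 and in ITT under the next. Because Treated is a subset of ITT, it inherits the ambiguity. The denominator of both primary tests is therefore not settled by the written rules.

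The study is single-arm and open-label and is tested against fixed performance goals, so membership decisions can be made with the outcome in view. Exclusion criterion 2 is an investigator's judgement that the subject is at risk of device or procedure complications. That judgement is related to both endpoints, so a complication could prompt a second look at eligibility.

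**Working it through.** **1. The rules side by side**

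| Subject | SAP 4.1 / protocol 12.2.1, screen failure | SAP 4.1 / protocol 12.2.1, ITT | Protocol 10.1 |
|---|---|---|---|
| Consented, clip placed, later found ineligible | Excluded | Kept | Not a screen failure by its definition; Screening and End of Study forms completed |
| Consented, eligible, clip planned, no study procedure | Not covered | Kept | Screen failure |
| Emergent, clip placed, consented afterwards, found ineligible | Excluded | Kept if counted as planned for a clip | As in the first row |

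The first row is a direct conflict. The second shows that 10.1 and ITT also differ. In the third, any ineligibility established after consent is necessarily established after clip use.

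**2. The plan's own figure**

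Inputs from SAP 3.1.3: exact test, alpha 0.05, n=217, goals 89% and 19%, expected rates 94% and 10%. The tests are one-sided by the form of the hypotheses.

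- Effectiveness: the smallest x with P(X ≥ x | 217, 0.89) ≤ 0.05 is x=201, with type I error 0.0492. Power is P(X ≥ 201 | 217, 0.94) = 84.1%.
- Safety: the largest y with P(Y ≤ y | 217, 0.19) ≤ 0.05 is y=31, with type I error 0.0426. Power is P(Y ≤ 31 | 217, 0.10) = 98.3%.

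Both meet the stated power of at least 80%, so the plan's figure reproduces.

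**3. Illustration: two disputed subjects**

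The number two is an assumption.

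*Dropped regardless of outcome (n=215).* The thresholds become 200 successes and 31 subjects with a related SAE.
- P(X ≥ 200 | 215, 0.89) = 0.0321
- P(Y ≤ 31 | 215, 0.19) = 0.0485

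Both stay within 0.05.

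*Up to two dropped, only unfavourable ones.* Start from 217 and allow removal of up to two failures, or of up to two subjects with a related SAE.
- Effectiveness passes if X ≥ 201 of 217, or X ≥ 201 of 216, or X ≥ 200 of 215. The loosest condition is X ≥ 200 among the original 217: P(X ≥ 200 | 217, 0.89) = 0.0788.
- Safety passes at n=215 if Y − 2 ≤ 31, that is Y ≤ 33 among the original 217: P(Y ≤ 33 | 217, 0.19) = 0.0879.

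| Exclusion rule | Effectiveness | Safety |
|---|---|---|
| None (n=217) | 4.9% | 4.3% |
| Two, outcome-neutral (n=215) | 3.2% | 4.9% |
| At most one, unfavourable only | 4.9% | 6.2% |
| At most two, unfavourable only | 7.9% | 8.8% |

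Example: 200 of 217 gives p=0.079 and misses the goal; 200 of 215, after two failures are removed, gives p=0.032 and meets it.

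**The case against.** The best defence is that the documents already point to a pre-procedure cut-off. Protocol 10.1 defines screen failure as not undergoing the study procedure. Carried into 12.2.1 and SAP 4.1, that meaning would not reach treated subjects. The sentence about the Screening and End of Study forms is data handling and does not order removal from analysis. There are only four eligibility criteria, and all can be judged at or before consent. Protocol 10.2 requires every enrolled subject to be accounted for, screen failures are recorded in the EDC, changes are audit-trailed, and section 14 requires deviations to be documented. Any removal would be visible.

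Much of this stands. Disputed subjects are likely to be few, and the sensible reading is available. But the analysis-set sections do not adopt the 10.1 definition. They use a different one based on eligibility, and 10.1 does not name a set for the tests.

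Three stronger readings are tempting and are not supported.

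- A reader might infer that a pre-procedure cut-off cannot work for emergent cases. That goes too far. Consent must precede study data collection, so the criteria can be checked at that point, before the 30-day outcome. What remains is that no cut-off is written for them.
- A reader might count the protocol 9.2 lead-in, under which such subjects "cannot be included in this study or will be excluded from this clinical study", as a further conflict. It is the general introduction to the exclusion criteria and does not address ineligibility discovered later.
- A reader might lean on the absence of an events committee. Such a committee would classify events, not decide who belongs to an analysis set.

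**Conclusion.** The concern holds as an unresolved contradiction in the analysis-set definitions, together with a missing assignment of a set to the two primary tests. It should be corrected before outcomes are seen, because the choice cannot credibly be pre-specified afterwards.

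The size is modest and conditional. If exclusions do not depend on outcome, two of them leave type I error within alpha. The rates of 7.9% and 8.8% are a worst case in which only unfavourable subjects are removed. A reader might infer that the plan permits or intends selective removal. No passage directs it, and those rates should not be read as the trial's actual error rates. They show only that two subjects can decide a borderline result while the rule for counting them is open.

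The figures assume one-sided exact tests at the 0.05 level in the current SAP text, 217 evaluable subjects, and two disputed subjects. The documents give no basis for that last number. The difference between ITT and Treated is not quantified; it may be small, since the continued enrollment objective refers to cases in which a MANTIS clip is selected.

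**What to change.** - **One screen-failure rule.** In protocol 10.1, protocol 12.2.1 and SAP 4.1, limit screen failure to consented subjects in whom no MANTIS clip use was attempted.
- **Retention.** Keep every consented subject with attempted clip use in follow-up and analysis, including those consented after an emergent procedure, subject to withdrawal under protocol 10.2. Record ineligibility found later as a protocol deviation.
- **Named primary set.** State that both primary tests are run in all continued-enrollment subjects with attempted clip use. Reword the ITT definition to match, and say openly that it moves from planned to attempted use: subjects planned but not attempted become screen failures, as 10.1 already implies.
- **Sensitivity analysis.** Report both tests in the Treated set.
- **Cross-reference.** Change 8.1 and 8.2 to protocol 9.1 and 9.2.

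The cost is wording in three sections and one set of sensitivity results, with no added subjects or visits. The downside is that a few ineligible subjects stay in the primary set and the success rate may be slightly lower. Using Treated as the primary safety set would also be defensible; what matters is that the choice is written down.

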5.1 Other Endpoints/Measurements

- Technical success at placement defined as ability to deploy the endoscopic clips in satisfactory position.
- Ability to anchor device, mobilize the tissue, and approximate defect edges for a secured closure.
- Post procedural bleeding, defined as a severe bleeding event that required hospitalization, a blood transfusion (>5 units), or another invasive intervention (angiographic or surgical) within 30 days after completion of the study clip placement procedure.
- For active bleeding hemostasis cases only
 - o Rate of patients requiring additional modalities of hemostasis.
 - Report of hemostasis of active bleeding 7 days after the index study procedure, and/or with additional clipping procedures to provide hemostasis of continued or recurrent bleeding within 7 days of the index study procedure

Baseline Data 5.2

Subject demographics and medical history will be summarized using descriptive statistics (e.g., mean, standard deviation, n, minimum, maximum) for continuous variables and frequency statistics for discrete variables.

5.3 **Procedure Data**

Procedure data including qualitative evaluation will be collected and reported using descriptive statistics (e.g., mean, standard deviation, n, minimum, maximum) for continuous variables and frequency statistics for discrete variables.

5.4 Post-Procedure Data

Post-procedure information will be collected as detailed in Table 10-1.1 Data Collection Schedule from the protocol and will be summarized using descriptive statistics for continuous variables (e.g., mean, standard deviation, n, minimum, maximum) and frequency statistics for discrete variables.

Interim Analyses

There will be no formal interim analyses performed.

92934442 C Page 10 of 12

5.6 Subgroup Analyses

Stratified analyses will include tabulating the primary and select secondary endpoints by gender, polyp location, polyp size, or use of periprocedural antithrombotic medications.

5.7 Justification of Pooling

The analyses will be performed using data pooled across institutions. An assessment of the poolability of patients across sites will be made by fitting generalized linear models with site as the factor of interest and the primary endpoints as the outcome variable.

5.8 Multivariable Analyses

Multivariable analyses may be performed to assess the effect of potential predictors on the primary endpoints and select secondary endpoints.

5.9 Changes to Planned Analyses

Any changes to the planned statistical analyses made prior to performing the analyses will be documented in an amended Statistical Analysis Plan approved prior to performing the analyses.

6 VALIDATION

All clinical data reports generated per this plan will be validated per 90702587, Global WI: Clinical Data Reporting Validation.

7 PROGRAMMING CONSIDERATIONS

7.1 Statistical Software

All statistical analyses will be done using The SAS System software, version 8 or higher (Copyright © 2000 SAS Institute Inc., SAS Campus Drive, Cary, North Carolina 27513, USA. All rights reserved).

7.2 Format of output

Results of analysis will be output programmatically to Word documents from SAS with no manual intervention. All output for the final statistical report will be in the form of a Word document containing tables, figures, graphs, and listings, as appropriate.

7.3 Rules and Definitions

- Binary event rates (proportions) will be reported on a per-patient basis.
- The last follow-up date will be the latest of the following dates for each patient: date of an adverse event, procedure date, follow-up visit date, and device event date.
- Serious Adverse Event will be defined as an adverse event that:
 - Led to death
 - Led to a serious deterioration in the health of the subject that either resulted in:
 - a life-threatening illness or injury, or
 - a permanent impairment of a body structure or a body function, or

- in-patient hospitalization or prolonged hospitalization (of an existing hospitalization), or
- medical or surgical intervention to prevent life-threatening illness or injury or permanent impairment to a body structure or a body function
- o Led to fetal distress, fetal death, or a congenital abnormality or birth defect.
- When calculating rates of adverse events, missing and partial dates will be handled as follows:

Partial Date Description	Action Taken
Entire onset date is missing	The procedure date will be used for the
	onset date.
The month and the day of the month are	January 1 will be used for the month and
missing but the year is available	day of the onset date. However, if the
	imputed date falls before the procedure
	date, then the procedure date will be used
	for the onset date.
Day is missing, but the month and year are	The 1 st will be used as the day of the onset
available	date. However, if the imputed date falls
	before the procedure date, then the
	procedure date will be used for the onset
	date.

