Device Deficiencies (including but not limited to malfunctions, use errors, and inadequacy in	Complete Device Deficiency CRF with all available new and updated information.	Within 3 calendar days of first becoming aware of the event. Reporting required through the end of the study	Within 3 calendar days of first becoming aware of the event. Reporting required through the end of the study
information supplied by the manufacturer, including labelling) Note: Any Study Device Deficiency that might have led to a serious adverse event if appropriate action had not been taken, intervention had not occurred, circumstances had	Provide all relevant source documentation (de-identified/ pseudonymized) for reported event.	Upon request of sponsor	Upon request of sponsor

Event Classification	Communication Method	Communication Timeline pre-market studies (21 CFR Part 812, MDCG 2020-10/1)	Communication Timeline post-market studies* (EU MDR 2017/745, MDCG 2020-10/1MEDDEV 2.12/1: GUIDELINES ON A MEDICAL DEVICE VIGILANCE SYSTEM)
been less fortunate is considered a reportable event.			
Adverse Event including Adverse Device Effects	Complete AE eCRF page, which contains such information as date of AE, treatment of AE resolution, assessment of seriousness and relationship to the device.	 In a timely manner (e.g. recommend within 10 business days) after becoming aware of the information Reporting required through end of study Upon request of sponsor 	Adverse Device Effects (or other key events of interest, e.g., Heart Failure): In a timely manner but not later than 30 business days after becoming aware of the information Adverse Events: In a timely manner but recommend within 30
	Provide all relevant source documentation (de-identified/ pseudonymized) for reported event.		business days after becoming aware of the information Reporting required through end of study. Upon request of sponsor

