	NOTE: If providing hemostasis to an active bleed requires possible additional hemostasis after the index study procedure for management of bleeding SAEs within 7 days ³⁶ of the index study procedure, then such bleeding SAEs are not counted for the Primary Safety Endpoint.	
Additional Endpoints	Technical success at placement defined as ability to deploy the endoscopic clips in satisfactory position.	
	2. Ability to anchor device, mobilize the tissue, and approximate defect edges for secured closure. (Group B only).	

MANTIS Clip Study		
	3. Post procedural bleeding, defined as a severe bleeding event that required hospitalization, a blood transfusion (>5 units), or another invasive intervention (angiographic or surgery) within 30 days after the study clip placement.	
	4. For active bleeding hemostasis cases only	
	a. Rate of patients requiring additional modalities of hemostasis.	
	b. Report of hemostasis of active bleeding 7 days after the index study procedure, defined as ability to stop the active bleed at the time of the study procedure and/or with additional clipping procedures to provide hemostasis of continued or recurrent bleeding within 7 days of the index study procedure	
Follow-up Schedule	Baseline	
	Procedure	
	30 day follow up (both Initial and Continued Enrollment Cohort)	
Study Duration	Enrollment is expected to be completed in approximately 18 months; therefore the total study duration is estimated to be approximately 19 months as Subjects will be on the study for up to 30 days.	
Key Inclusion Criteria	Subject indicated for endoscopic clipping per local standard of practice.	
	2. Willing and able to comply with the study procedures and provide written informed consent to participate in the study.	
	NOTE: Hemostasis and closure can be needed in the setting of complications such as perforations or acute bleeding that are typically rare and sometimes emergent. In such circumstances consenting the patient before the procedure is not feasible and consent shall be obtained from the patient after the procedure but before any study data is collected.	
Key Exclusion Criteria	1. Subjects who are currently enrolled in another investigational study that would directly interfere with the current study, without prior written approval from the sponsor.	

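### If the 7-day exclusion is timed by SAE onset, the SAP's earliest-date rule can move a late bleeding SAE into the window that the primary safety endpoint does not count

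*SAP*

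**What the plan says.** The primary safety endpoint is the rate of SAEs related to the clip or to the study portion of the procedure, tested against a 19% performance goal. SAP 3.1.2 carves out one class of event. The condition is "If providing hemostasis to an active bleeding in Group A requires possible additional hemostasis after the index study procedure for management of bleeding SAEs", and the consequence is "bleeding SAEs within 7 days of the index study procedure, then such bleeding SAEs are not counted for the Primary Safety Endpoint". SAP 1 carries the same note without the Group A limit ("If providing hemostasis to an active bleed requires possible additional hemostasis after the index study procedure for management of bleeding SAEs").

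SAP 7.3 handles incomplete dates: "When calculating rates of adverse events, missing and partial dates will be handled as follows".

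- Whole date missing: "The procedure date will be used for the" onset date.
- Only the year known: January 1, or the procedure date if that is later.
- Only the day missing: the first of the month, or the procedure date if that is later.

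No exception is written for the primary safety endpoint or for the 7-day window. The same section states "Binary event rates (proportions) will be reported on a per-patient basis".

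Neither document says which date the 7 days measure. SAP 5.1 uses similar words next to the repeat treatment ("additional clipping procedures to provide hemostasis of continued or recurrent bleeding within 7 days of the index study procedure"), so the window could be timed by SAE onset or by the additional hemostasis.

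**The concern.** Imputing the earliest date is normally conservative for safety, because it keeps an event inside the counted period. Here the early period is the uncounted one, so the same rule works in the sponsor's favor.

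Take an active bleed in Group A clipped on the 3rd of a month. A related bleeding SAE that needs additional hemostasis starts on the 20th (day 17), and the day is not recorded. SAP 7.3 sets the onset to the 1st, then resets it to the procedure date because the 1st is earlier. The event becomes day 0 and, if the window is timed by onset, is not counted.

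The reverse cannot happen. The imputed date is never later than the true date, so a true day 0-7 event stays inside the window. Within this carve-out, imputation error can lower the tested rate and never raise it.

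**Working it through.** **Inputs.** Goal 19%, expected rate 10%, exact test, alpha 0.05 and 217 evaluable subjects (SAP 3.1.3). Alpha 0.025 is shown as well, because the SAP revision history says the calculation used it. Follow-up is 30 days with a visit window of ±5 days (protocol 11.7 and 11.8). The date rules are those of SAP 7.3.

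**The plan's own figure.** With X the number of patients with a counted event, the safety test passes if X is at or below the largest c for which P(X ≤ c | n = 217, p = 0.19) ≤ alpha.

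| One-sided alpha | Limit c | Size at 19% | Power at 10% |
|---|---|---|---|
| 0.05 | 31 | 0.0426 | 0.9830 |
| 0.025 | 29 | 0.0181 | 0.9565 |

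The stated power of at least 80% is reproduced for safety at either alpha.

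**How often the rule moves a late event.** Cross all 365 procedure dates in a year with every onset day, treating each combination as equally likely (an assumption). Apply SAP 7.3 and count imputed onsets within 7 days of the procedure.

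| True onset | Day missing | Month and day missing | Whole date missing |
|---|---|---|---|
| Days 8-30, moved in | 5083/8395 = 61% | 8119/8395 = 97% | 8395/8395 = 100% |
| Days 8-35, moved in | 5348/10220 = 52% | 9814/10220 = 96% | 10220/10220 = 100% |
| Days 0-7, moved out | 0/2920 | 0/2920 | 0/2920 |

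Not every incomplete date matters. For a procedure on 10 March and onset on 5 April (day 26) with the day missing, the imputed date is 1 April (day 22), and the event is still counted.

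**Effect at the planned 10% rate.** About 0.10 × 217 ≈ 22 event patients are expected. Lost events can change the conclusion only in trials that would otherwise fail. That chance is 1 − 0.9830 = 1.7% at 0.05, and 4.3% at 0.025 (P(X > 29) = 0.0435). These are ceilings, however many events are lost. If m event patients are omitted, the chance of turning a fail into a pass is P(c < X ≤ c + m | p = 0.10).

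| Patients omitted | 0.05 | 0.025 |
|---|---|---|
| 1 | 0.7% | 1.6% |
| 2 | 1.1% | 2.7% |
| 3 | 1.4% | 3.3% |

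**Effect at a true rate of 19%.** Type I error becomes P(X ≤ c + m | p = 0.19).

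| Patients omitted | 0.05 | 0.025 |
|---|---|---|
| 0 | 4.3% | 1.8% |
| 1 | 6.2% | 2.8% |
| 2 | 8.8% | 4.3% |
| 3 | 12.1% | 6.2% |

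The documents give no rate of missing dates. The cases of 1 to 3 omitted patients are illustrations, not forecasts.

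**The case against.** The strongest objection is that this will hardly ever happen. Six things must coincide: an active bleed in Group A, a related bleeding SAE, a need for additional hemostasis, true onset after day 7, an incomplete onset date, and a window timed by onset. The plan also works against incomplete dates. The AE form is one "which contains such information as date of AE, treatment of AE resolution" (protocol 19.4), SAEs have reporting deadlines, the database is queried (13.1), monitors check the records (17), and sponsor safety staff review events as they are reported (21.1). A bleed that needs repeat hemostasis should leave a dated treatment record.

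For scale, suppose 5-30% of the 22 expected event patients have a late Group A bleed needing more hemostasis, and 1-5% of those have incomplete dates. Both ranges are assumptions. The expected number is then 22 × 0.05 × 0.01 = 0.01 to 22 × 0.30 × 0.05 = 0.33 patients, before allowing for dates that do not move the event.

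This stands as a statement of size: the effect is probably very small, and the 12.1% should not be read as a realistic risk. It does not remove the fault, because those controls make incomplete dates rare without ruling them out, and the written rule then acts in one direction.

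Two further points stand. If the window is timed by the additional hemostasis, SAP 7.3 alone excludes nothing and only the ambiguity remains. And any remedy that counts unresolved events will count some that are truly early. That is a choice of the conservative direction, and it has a cost.

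**Conclusion.** The point holds, as an optional improvement. On the onset reading, a stated SAP rule can remove a countable late SAE from a primary endpoint and can never add one. The 61%, 97% and 100% apply only to events that already meet every other condition, and they assume uniform onset on days 8-30. The number of affected patients is unknown and probably close to zero. At the planned 10% rate the conclusion changes at most 1.7% of the time (0.05) or 4.3% (0.025).

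The consequence is limited in two other ways. A patient with another counted related SAE stays counted, because rates are per patient, and the omitted event is still reported as an SAE. The ambiguity about which date the 7 days measure exists whether or not any date is missing. It should be settled before the data are seen.

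**What to change.** 1. In SAP 3.1.2, state which date the 7 days measure: the SAE onset or the additional hemostasis.
2. In SAP 7.3, add that an imputed onset date is not used to apply the 7-day exclusion from the primary safety endpoint. A bleeding SAE is excluded only when the recorded date parts or other dated records (for example, the date of the additional hemostasis, the hospitalization or the AE report) show that it fell within 7 days of the index procedure. Otherwise it is counted.

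The classification of delayed bleeding for the effectiveness endpoint should stay as it is.

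The cost is two SAP sentences and one programming condition. The observed SAE rate may also be slightly less favorable, because some true day 0-7 events with incomplete dates would now be counted. Recorded date parts alone place 14.8%, 1.2% and 0% of such events inside the window (day, month and day, or whole date missing). The share newly counted is therefore (1 − share with another dated record) × (0.8521, 0.9877 or 1). The record shares below are assumptions.

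| Share with another dated record | Day missing | Month and day missing | Whole date missing |
|---|---|---|---|
| None | 85% | 99% | 100% |
| Half | 43% | 49% | 50% |
| 90% | 9% | 10% | 10% |
| All | 0% | 0% | 0% |

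Querying every incomplete SAE date before database lock would shrink this cost further, but it would not replace a rule for dates that stay unresolved.
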